### 5.3. RETESTS AND UNSCHEDULED VISITS DATA

Generally, data recorded at the nominal visit will be presented for by-visit summaries.

Unscheduled measurements will not be included in by-visit summaries, but will contribute to the best/worst case

---

Document:	\\ieedc-vnasc01\Biosdata\Archigen\SAIT101\YWA21301\Biostatistics\Documentation\SAP		
Author:		Version Number:	V2.0
		Version Date:	13Feb2019

Template No: CS\_TP\_BS016 Revision 4  
Effective Date: 01Apr2016

Reference: CS\_WI\_BS005

value where required (e.g. shift table).

In the case of a retest (same visit number assigned), the latest available measurement for that visit will be used for by-visit summaries.

Listings will include scheduled, unscheduled, retest and early study discontinuation data.

## 5.4. STATISTICAL TESTS

The default significant level will be 0.05 for statistical tests; the two-sided 90% confidence intervals (CI) will be calculated for PK analyses and 95% CI for efficacy analyses, unless if specified otherwise.

## 5.5. COMMON CALCULATIONS

For quantitative measurements, change from Baseline at Visit X will be calculated as:

- Change at Visit X = Test Value at Visit X – Baseline Value

The time from Date of Event A to Date of Event B (years) is calculated as:

- $(\text{Date of Event B} - \text{Date of Event A} + 1) / 365.25$ .

The time from Date of Event A to Date of Event B (months) is calculated as:

- $(\text{Date of Event B} - \text{Date of Event A} + 1) / 30.4375$ .

## 5.6. SOFTWARE VERSION

All derivations (except PK and PD parameter calculations), statistical analyses, summaries and listings will be generated using SAS® Version 9.4 or higher.

Noncompartmental PK parameter calculations will be performed using Phoenix WinNonlin® 6.4 or higher, and/or SAS® Version 9.4 or higher. Graphics may be prepared using the same versions of SAS®, or Phoenix WinNonlin®, or with SigmaPlot® 12.5, or higher.

# 6. Statistical Considerations

## 6.1. MULTICENTER STUDIES

This study will be conducted by multiple investigators at multiple centers internationally.

Center pooling will be carried out across all centers for use in statistical summaries for this study.

## 6.2. MULTIPLE COMPARISON/MULTIPLICITY

No multiple comparison adjustment will be used for main efficacy analysis, since there is only one main efficacy analysis for change from baseline at Week 24. No multiple comparison adjustment will be used either for the PK analyses since the significance level is pre-specified at 10% (two-sided) to show equivalence within pre-specified limits, and the overall power for the PK equivalence assessment accounts for the multiple testing.

---

Document: \\ieedc-vnasc01\Biosdata\Archigen\SAIT101\YWA21301\Biostatistics\Documentation\SAP  
Author: Version Number: V2.0

Version Date: 13Feb2019

Template No: CS\_TP\_BS016 Revision 4  
Effective Date: 01Apr2016

Reference: CS\_WI\_BS005

### 6.3. MISSING DATA

Partial date will be imputed for the identification of treatment-emergent adverse events (TEAEs), prior/concomitant medication, calculation of demographic information and medical history. Rules will be discussed in [Appendix 1](#) of this SAP.

Main efficacy data will be handled in Section 15.1.2 and 15.2.2 of this SAP.

Missing data for will be handled as described in Section 13 for PK and Section 14 for PD.

Unless otherwise specified, missing data will not be imputed in this study.

### 6.4. DATA EXTRACTION RULE

For DSMB, only data up to the DSMB target time point will be included. Specific data extraction rules are described in [Appendix 3](#).

## 7. Output Presentations

The TLF templates provided with this SAP describe the conventions for the presentation of data in outputs, and the format and content of the summary tables, figures and listings.

Some minor modifications may be necessary to the planned design of tables, figures, and listings to accommodate data collected during the actual study conduct.

## 8. Disposition and Withdrawals

The number and percentage of patients who were screened and randomized will be presented. For the patients who left the study prior to randomization, a summary will be presented for the reasons of screen failure. For the patients who were randomized, summaries will be presented for the number and percentage of patients as follows:

#### Analyses by Week 24:

- Met eligibility of Part A or not
  - Received any infusion in Part A
  - Not received any infusion in Part A
- 1st Randomized
- Received at least one infusion of study drug
- Prematurely discontinued treatment during Part A
  - Prematurely stopped and not restarted the first infusion (by reason for premature discontinuation of study treatment, which will be captured from “End of Treatment” of CRF)
  - Only completed the first infusion (by reason for premature discontinuation of study treatment, which will be captured from “End of Treatment” of CRF)
  - Prematurely stopped and not restarted the second infusion (by reason for premature discontinuation of study treatment, which will be captured from “End of Treatment” of CRF)
  - Prematurely stopped, then restarted, but not completed the second infusion (by reason for premature discontinuation of study treatment, which will be captured from “End of Treatment” of CRF)
- Withdrew early from Part A of the study
  - Lost to follow-up

---

Document: \\ieedc-vnasc01\Biosdata\Archigen\SAIT101\YWA21301\Biostatistics\Documentation\SAP

Author:

Version Number:

V2.0

Version Date:

13Feb2019

Template No: CS\_TP\_BS016 Revision 4  
Effective Date: 01Apr2016

Reference: CS\_WI\_BS005

- Study terminated by sponsor
- Trial site terminated by sponsor
- Withdrawal of content
- Other
- Missing
- Completed Part A of the study-- received assessments at Week 24 without study treatment discontinuation (required to receive two complete study infusions of Part A) or study withdrawal during Part A

#### **Analyses by Week 52:**

- All items for analyses by Week 24 above
- Met eligibility of Part B or not (which will be captured from “Re-treatment” of CRF)
  - Received any infusion in Part B
  - Not received any infusion in Part B
- Re-randomized
- Received at least one infusion of study drug during Part B
- Prematurely discontinued treatment during Part B
  - Prematurely stopped and not restarted the first infusion (by reason for premature discontinuation of study treatment, which will be captured from “End of Treatment” of CRF)
  - Only completed the first infusion (by reason for premature discontinuation of study treatment, which will be captured from “End of Treatment” of CRF)
  - Prematurely stopped and not restarted the second infusion (by reason for premature discontinuation of study treatment, which will be captured from “End of Treatment” of CRF)
  - Prematurely stopped, then restarted, but not completed the second infusion (by reason for premature discontinuation of study treatment, which will be captured from “End of Treatment” of CRF)
- Withdrew early from Part B of the study
  - Lost to follow-up
  - Study terminated by sponsor
  - Trial site terminated by sponsor
  - Withdrawal of content
  - Other
  - Missing
- Completed Part B of the study—received assessments at Week 52 without study treatment discontinuation (required to receive two complete study infusions of Part B) or study withdrawal during Part B
- Completed the study—received at least the first course of study drug and assessments at Week 52

Protocol deviations (as defined in section 4.10) will be presented by treatment group for the RAN.

Number (%) of subjects in the analysis sets and exclusion reason will be summarized by treatment group for the RAN.

## **9. Demographic and other Baseline Characteristics**

Subject demographics and baseline characteristics will be summarized by treatment group for the RAN, FAS, PKS and PP. If the FAS is as same as the RAN, then only the RAN will be displayed. Continuous variables will be summarized with descriptive statistics (n, mean, SD, median, minimum and maximum). Categorical variables will be summarized with counts and percentages.

To evaluate differences among Mexican site 10703 and all other sites between baseline characteristics,

---

Document:	\\ieedc-vnasc01\Biosdata\Archigen\SAIT101\YWA21301\Biostatistics\Documentation\SAP	
Author:	Version Number:	V2.0
	Version Date:	13Feb2019

Template No: CS\_TP\_BS016 Revision 4  
Effective Date: 01Apr2016

Reference: CS\_WI\_BS005

additional analyses of baseline characteristics will be added.

- Overall total (all treatments) for site 10703
- Overall total (all treatments) for all sites except site 10703
- Overall total (all sites/treatments)

The following demographics and baseline characteristics will be summarized appropriately for the study:

### Demographics

- Age (years) – calculated to date of Informed Consent
- Age group – 18-60 years, >60 years
- Gender – Female, Male
- Ethnicity– Hispanic or Latino, Not Hispanic or Latino, Not Reported, Unknown
- Race – American Indian or Alaska Native, Asian, Black or African American, Native Hawaiian or other Pacific Islander, White, Other, Unknown, Not Reported
- Weight (kg) at Baseline
- Height (cm) at Baseline
- BMI (kg/m^2) at Baseline – derived as weight (kg)/(height (m))

### Baseline Characteristics

- Disease duration (years) – calculated initial diagnosis date of RA relative to date of informed consent
- Childbearing potential – Yes, No
- Duration of Methotrexate (MTX) use (months) – calculated relative to date of Day 1; MTX identified using the following Preferred Term: "METHOTREXATE", "METHOTREXATE SODIUM"
- Number of previous disease-modifying anti-rheumatic drugs (DMARDs) except MTX – 0, 1, 2, 3, More than 3

DMARDs will be coded using WHO DRUG dictionary DDE Mar 01, 2016 or higher and identified using the following Anatomical Therapeutic Chemical Classification (ATCC) code: L04AA, A07EC, M01CA, M01CB, M01CC, M01CX, J01AA, P01BA

- Baseline rheumatoid factor
- Baseline anti-CCP antibodies
- Baseline C-reactive protein (CRP) (mg/L)
- Baseline erythrocyte sedimentation rate (ESR) (mm/hr)
- Baseline swollen joint count (SJC)
- Baseline tender joint count (TJC)
- Baseline patient global assessments VAS score (mm)
- Baseline physician global assessment VAS score (mm)
- Baseline patient pain assessment VAS score (mm)
- Baseline HAQ-DI score
- Baseline DAS28-CRP score
- Baseline DAS28-ESR score

The HAQ-DI questionnaire contains 20 questions classified into 8 categories (dressing & grooming, arising, eating, walking, hygiene, reach, grip, and activities) with 2 to 3 questions for each category. The scoring for each result should be as below: 0 = Without ANY Difficulty; 1 = With SOME Difficulty; 2 = With MUCH Difficulty; 3 = UNABLE To Do.

The HAQ-DI score will be calculated as follows:

- 1) Determine the highest score among 2 to 3 questions for 8 categories
- 2) Adjust for use of aids/devices and/or help from another person excluding 'Other' items - Increase the score

---

Document:	\\ieedc-vnasc01\Biosdata\Archigen\SAIT101\YWA21301\Biostatistics\Documentation\SAP
Author:	Version Number: V2.0
	Version Date: 13Feb2019

Template No: CS\_TP\_BS016 Revision 4  
Effective Date: 01Apr2016

Reference: CS\_WI\_BS005

of 0 or 1 to 2, but if the score is 2, it remains 2 and if the score is 3, it remains 3

Any aids or devices	Category
Cane, Walker, Crutches, Wheelchair	Walking
Devices used for dressing	Dressing & Grooming
Built up or special utensils	Eating
Special or built up chair	Rising
Raised toilet seat, Bathtub seat, Bathtub bar, Long-handled appliances in bathroom	Hygiene
Long-handled appliances for reach	Reach
Jar opener	Grip
Errands and chores	Common Daily Activities

3) If score can't be determined in more than 2 categories, then HAQ-DI score will be considered as missing, i.e. at least score for 6 of 8 categories.

4) HAQ-DI score is calculated as the summed category scores divided by the number of categories answered (range 6-8).

## 10. Medical and Surgical History and Continuing Medical Condition

Medical and surgical history, continuing medical conditions will be coded using Medical Dictionary for Regulatory Activities central coding dictionary, Version 19.0 (MedDRA 19.0) or higher, and summarized by system organ class (SOC) and preferred term (PT) for the RAN. Continuing medical condition was identified the items with 'Ongoing with treatment' or 'Ongoing without treatment' status in the Medical History page of the eCRF.

## 11. Medications and Procedures

### 11.1. MEDICATIONS

Prior and/or concomitant medications will be coded using WHO DRUG dictionary DDE Mar 01, 2016 or higher and Anatomical Therapeutic Chemical Classification (ATCC).

See [Appendix 1](#) for the handling of partial dates for medications, in the case where it is not possible to define a medication as prior or concomitant, the medication will be classified by the worst case; i.e. concomitant.

- 'Prior' medications are medications which started prior to the first of study.
- 'Concomitant' medications are medications which started on or after the first of study, and ended on or after the first dose of study drug or are ongoing at the end of the study.

Medications will be considered as "prior", if answer of "Was the medication/therapy taken prior to the study?" are yes, and if answers are no then they will be considered as concomitant medications.

'Rescue' medication is defined as the use of non-biologic DMARDs, after Week 16 of the study and is identified as 'Rescue medication' for 'Indication' on eCRF. Patients with any rescue medication are summarized by visit and treatment group. Time to first incidence of rescue medication after Week 16 of the study will be estimated for each treatment group and presented using Kaplan-Meier methods. Kaplan-Meier plots will also be presented.

Document:	\\ieedc-vnasc01\Biosdata\Archigen\SAIT101\YWA21301\Biostatistics\Documentation\SAP	
Author:	Version Number:	V2.0
	Version Date:	13Feb2019

Template No: CS_TP_BS016 Revision 4	Reference: CS_WI_BS005
Effective Date: 01Apr2016	

In addition, percentiles of time without rescue medication will be presented.

The following formula will use to calculate the time-to-event variable in weeks = floor ((event occur date - date of first study drug + 1)/(7))

Prior medication, concomitant medications and rescue medications will be summarized will be summarized by Anatomic Therapeutic Chemical (ATC) pharmacological sub-class (4th level) for the SAF. All medication used will be listed.

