**Table 5 List of Medications Permitted During the Study**

Treatment	Restriction
Methotrexate	Patients must be taking MTX at a dose of 7.5-25 mg/week (oral or parenteral) throughout the study and for at least 12 weeks prior to study entry. Patients receiving a lower dose of MTX (<10 mg/week) should be doing so as a result of a documented evidence of intolerance to higher doses of MTX. The dose and route of administration should remain stable from 4 weeks prior to randomization and where possible, throughout the entire study period.
Folic or folinic acid	Patients must be taking oral folic or folinic acid or equivalent during the entire study (mandatory co-medication for MTX treatment), according to local standards and availability. The dosing regimen is at the Investigator's discretion.
Antipyretics	Patients will receive an antipyretic, e.g., paracetamol or equivalent, 30 to 60 minutes before each drug infusion.
Antihistamines	Patients will receive an antihistamine, e.g., diphenhydramine or equivalent, 30 to 60 minutes before each drug infusion.
Oral corticosteroids	If receiving current treatment with oral corticosteroids at the time of Screening ( $\leq 10$ mg/day prednisone or equivalent), the dose must remain stable during the 4 weeks prior to Day 1. Increases in corticosteroids for treatment of RA are not allowed over the study period and should be avoided (see Section 3.2.5). Reductions in the dose of corticosteroids will be allowed as clinically required only for safety reasons.
Intravenous or intramuscular corticosteroids	Use of i.v. or intramuscular corticosteroids for RA will be considered worsening of a patient's condition from Baseline and should be recorded as an AE in the eCRF. The only exception will be the administration of 100 mg i.v. methylprednisone or equivalent within 30 minutes before each infusion as part of the study procedures.

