### **6.6.3 Concomitant Medication**

The incidence of concomitant medications will be summarized for the Safety Analysis Set by generic term coded with the World Health Organization-Drug Dictionary (WHO-DD) Enhanced, overall and by treatment group.

To allow assessment of concomitant medication that might affect the efficacy outcomes, counts will be presented for each treatment group at each visit of patients receiving any rescue medication at that visit; counts of patients receiving any rescue medication will also be presented during the study. Rescue medication is defined as the use of non-biologic DMARDs, after Week 16 of the study. Time to first incidence of rescue medication after Week 16 of the study will be estimated for each treatment group and presented using Kaplan-Meier methods. Kaplan-Meier plots will also be presented. In addition, percentiles of time without rescue medication will be presented.

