			
canceled and no unblinded at W24.
 
Section 4.3-FAS: Per agreement during blinded data review meeting 1, omit criteria of eligible for Part A or not while excluding patients from the FAS.
 
Section 4.5-PP: Per agreement during blinded data review meeting 1, if patients who were ineligible for Part A, they will be excluded from the PP set.
 
Section 9: added tables for baseline characteristics by site 10703 and other sites.
 
Section 13.2: Added two impact analyses added.
 
Section 15.2.2 adjustment of ESR: If ESR=0, it will be adjusted as <math>\ln(\text{ESR}+1)</math> while calculating DAS28-ESR, i.e. <math>\ln(1)=0</math>
 
Section 15.3.3: added line chart for changes from baseline of DAS28-CRP and bar chart for ACR20/50/70, which already existed in SHELL.
 
Section 15.3.3.: added above two figures for site 10703 per sponsor request.
 
Section 15.2.7: an impact analysis was added for site 10703 to evaluate impact of the site on the main efficacy analysis.

Draft 1.04	31Jan2019		
Section 4.5: Updated definition of PP set and omitted PP2 set.
 
Section 8: Updated disposition summary per agreement on BDR1 meeting
 
Section 15.2.5: Added comparison for MabThera vs Rituxan as one of exploratory analysis
 
Section 15.2.6: Removed sensitivity analyses due to protocol deviation
 
Section 15.2.7: had been adjusted to 15.2.6 in main context
 
Section 16.1: Updated definition of TEAE, i.e. no limit of end date
 
Section 11.1 and Appendix 1: prior and concomitant are derived by answer of CRF (Was the medication/therapy taken prior to the study? Yes=prior, No=concomitant)

Draft 1.05	12Feb2019		
Section 2.6: Added immunogenicity analyses.
 
Section 4: Added clarification for PK and PD analysis sets.
 
Section 9: Updated analysis for demographic and other baseline characteristics for overall

Document: \\ieedc-vnasc01\Biosdata\Archigen\SAIT101\YWA21301\Biostatistics\Documentation\SAP  
 Author: Version Number: V2.0  
 Version Date: 13Feb2019

Template No: CS\_TP\_BS016 Revision 4 Reference: CS\_WI\_BS005  
 Effective Date: 01Apr2016

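### SAP 11.1 has no class for a drug started before the study and continued through dosing, so background methotrexate and other continuing therapy is left out of the concomitant-medication table.

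*SAP*

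**What the plan says.** SAP 11.1 gives the rule twice.

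- **By dates.** Prior: "medications are medications which started prior to the first of study", with no condition on when the drug stopped. Concomitant: "medications which started on or after the first of study, and ended on or after the first dose of study drug", or still ongoing when the study ends.
- **By eCRF answer.** One question asks whether the drug was taken before the study. Yes makes it prior; "if answers are no then they will be considered as concomitant medications". The SAP modification history records the same rule for the 31 January 2019 draft: "prior and concomitant are derived by answer of CRF (Was the medication/therapy taken prior to the study? Yes=prior, No=concomitant".

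There is one fallback, to concomitant: "in the case where it is not possible to define a medication as prior or concomitant, the medication will be classified by the worst case". Appendix 1 of the SAP imputes partial medication dates and adds no rule for drugs that span the first dose.

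On background therapy, Protocol Table 5 says: "Patients must be taking MTX at a dose of 7.5-25 mg/week (oral or parenteral) throughout the study". Protocol 3.2.5 counts continuing MTX among the patient's concomitant medications. Protocol 6.6.3 plans the incidence of concomitant medications on the Safety Analysis Set, overall and by treatment group.

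**The concern.** A drug that spans the first dose is both prior and concomitant in the ordinary sense of the words. The SAP allows only one label and gives the first. Followed exactly, it produces a concomitant-medication table without the therapy that the protocol requires or permits patients to continue.

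What is at stake is the descriptive picture of treatment alongside study drug. In a three-arm similarity trial a reader will want to see whether corticosteroid and NSAID use during treatment was alike across arms, and that table is where they will look. Under SAP 3.1, the third and later DSMB analyses also draw on SAP sections 8 to 12, so the same table reaches the safety reviewers.

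**Working it through.** The plan states no figure to reproduce. The check traces the rule for each type of drug, with one piece of arithmetic on timing.

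**Inputs**
- MTX before Day 1: at least 12 weeks (Protocol 3.4.2, criterion 4) = 12 × 7 = 84 days.
- Longest screening period: 60 days (Protocol 3.6.1.1); ordinary screening period: 30 days.
- Oral corticosteroid dose stable for 4 weeks before Day 1 = 28 days; NSAID dose stable for 3 weeks = 21 days (Protocol 3.2.5 and 3.4.2).

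**MTX.** 84 − 60 = 24. An eligible patient's MTX starts at least 24 days before screening can open. Whether the eCRF question means before consent or before first dose, the answer is yes and MTX is prior only. Under the date definitions it fails the first condition for concomitant (a start on or after study start), even if it is still being taken at Week 52.

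**Folic or folinic acid.** It is a compulsory companion to MTX during the study, but the inclusion criterion asks for willingness to take it and sets no lead-in. Where it was already taken with MTX, it is prior only. Where it is first started on study, it counts as concomitant.

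**Oral corticosteroids and NSAIDs.** These are optional, and the stable-dose periods of 28 and 21 days are shorter than a 30-day screening period. Timing alone therefore does not settle the class. A drug already in use at Screening is answered yes and is prior only. One begun during screening depends on what the eCRF question means by the study, which SAP 11.1 leaves undefined.

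**Drugs newly started after first dose.** The answer is no, so they are concomitant, as they should be.

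**Fallback.** It applies only where the class cannot be determined. A clear yes determines it, so the fallback never reaches background MTX.

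**What remains visible.** SAP 11.1 also summarizes prior medications on the Safety Analysis Set and lists all medications. SAP section 9 summarizes duration of MTX use and the number of earlier DMARDs other than MTX. The prior table, however, holds both drugs withdrawn under Protocol Tables 4 and 6 and drugs continued through the study, and nothing in it separates the two.

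**The case against.** The strongest reply is that little is lost. The drugs are still reported in the prior table and listings. A corrected table would show MTX at about 100% in every arm, and since no dose summary is planned it could not show an imbalance in MTX dose. The yes/no rule was adopted deliberately. Prohibited medication is handled through protocol-deviation review for the per protocol set (SAP 4.5 and 4.8). All of this stands, and it limits the point to descriptive reporting. It does not make the table right: the prior table cannot show which corticosteroids or NSAIDs were taken on treatment, and SAP 2.6 does not list this narrowing as a change from protocol.

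Three stronger readings are tempting and are not supported.

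- **That arm imbalance in background therapy would be hidden altogether.** Use at entry appears in the prior table, and on-study use can be recovered from the listings. It is missing only from the summary tables.
- **That the rule defeats a protocol aim of judging effects on efficacy.** Protocol 6.6.3 has the phrase "To allow assessment of concomitant medication that might affect the efficacy outcomes", but the sentence goes on to specify counts of rescue medication by arm and visit. SAP 11.1 identifies rescue drugs from the eCRF indication field and summarizes them separately, so that aim is met.
- **That corticosteroids and NSAIDs are mandatory background treatment.** They are continued only if already in use. What Protocol 3.2.5 makes mandatory for them is a stable dose in Part A.

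**Conclusion.** The rule in SAP 11.1 is wrong as written. It never counts a drug started before the study and continued through dosing as concomitant, contrary to Protocol 3.2.5, and the incidence table planned in Protocol 6.6.3 would omit that therapy.

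For MTX the table would show close to 0% where the true on-study figure should be about 100%. This assumes that sites keep a continuing drug as one eCRF record. If a dose or route change is entered as a new record answered no, the figure could rise from 0% to at most the proportion of patients with such a change. The documents do not give that proportion or the eCRF completion guidelines. For corticosteroids and NSAIDs the shortfall equals the proportion of patients whose only use during treatment continues from before the study, which is also not given.

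The importance is low. Rescue-medication summaries, the PK analysis and the main efficacy analysis do not use the flag, and no conclusion on equivalence changes.

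**What to change.** In SAP 11.1, replace both versions of the rule with one based on dates:

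- prior if taken before the first dose of study drug;
- concomitant if taken on or after the first dose (stop date on or after first dose, or ongoing), whatever the start date;
- a drug may carry both flags;
- replace the incomplete study-start reference in the two date definitions with the first dose of study drug.

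The worst-case fallback and the Appendix 1 date imputation can stay, and they then serve a purpose in classification. The cost is one derivation rule and a rerun of the prior and concomitant tables, including those supplied to the DSMB. No new data item should be needed: Protocol 3.12 already requires dose, frequency and dates of concomitant medications in the eCRF from Visit 1.
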